2. STUDY OBJECTIVES

2.1. Primary objective:

- To evaluate the safety and efficacy of adding CD24Fc to COVID-19 best available treatment by comparing COVID-19 disease status improvement time between CD24Fc and placebo arms within 28 days.

2.2. Secondary objectives:

- Secondary objectives are to compare, for each treatment arm, proportion of patients who died or had respiratory failure (defined as the need for mechanical ventilation, ECMO, non-invasive ventilation, or high flow oxygen devices), the time to disease progression, rate of all-cause death, proportion of death or respiratory failure, rates of hospital discharge time, rate of duration of mechanical ventilation, duration of mechanical ventilation, use of pressors, rate of duration of extracorporeal membrane oxygenation, rate of duration of supplemental oxygen, the length of hospital stay, and the changes in absolute lymphocyte count and markers of inflammation.

2.3. Exploratory objectives:

- To explore the effect of CD24Fc treatment of COVID-19 on systemic steroid dosage, inflammatory cytokine changes, D-dimer level changes, lymphocyte subtype distribution and T lymphocyte activation and exhaustion markers.
- To explore the effect of CD24Fc in pulmonary function, inflammatory markers, cardiac function, liver enzymes and renal function.

2.4. Primary Endpoints:

- Time to improvement in clinical status: the time (days) required for improvement from scale 2 - 4 to scale ≥ 5 or above that is sustained without a drop to below 5 based on NIAID ordinal scales ([Appendix A](#)) within 28 days from randomization.

2.5. Secondary Endpoints:

- Proportion of patients who died or had respiratory failure, defined as the need for mechanical ventilation, ECMO, non-invasive ventilation, or high flow oxygen devices, at Day 29
- Time to disease progression in clinical status: the time (days) for progression from scale 3 or 4 to scale 1 or 2 based on the NIAID ordinal scale within 28 days from randomization.
- All cause mortality at Day 15 and Day 29
- Proportion of clinical relapse, as defined by rate of return to oxygen support for more than 1 day within 28 days from randomization after initial recovery

- Conversion rate of clinical status on Day 8 (proportion of subjects who changed from “scale 2, 3 or 4” to “scale 5 or higher” in the NIAID ordinal scale)

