- Conversion rate of clinical status on Day 15 (proportion of subjects who changed from “scale 2, 3 or 4” to “scale 5 or higher” in the NIAID ordinal scale)
- The discharge from hospital time
- Duration of mechanical ventilation (IMV, NIV) (days)
- Duration of pressors (days)
- Duration of extracorporeal membrane oxygenation (days)
- Duration of oxygen therapy (oxygen inhalation by nasal cannula or mask) (days)
- Length of hospital stay (days)
- Absolute lymphocyte count
- D-dimer concentration in the plasma

2.6. **Exploratory endpoints**

- Effect of CD24Fc on systemic steroid usage.
- Effect of CD24Fc on cytokine levels.
- Effect of CD24Fc on lymphocyte subtype distribution.

2.7. **Safety evaluation**

- Adverse events, vital signs, physical examination, laboratory tests (blood routine, blood biochemistry, coagulation function, urine routine), ECG.

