For the primary endpoint, during the observation period, an improvement from NIAID scale 2, 3 or 4 to scale 5 or above, if sustained without a drop below 5, is considered as an event. The days from the randomization to the first time point of such improvement will be defined as time of improvement. Additional follow-up can be used to determine clinical improvement events.

Subjects who do not withdraw or do not experience improvement will be censored on the actual date of the D29 visit.

Subjects without improvement but lost to follow-up will be censored on the last date of follow-up.

Subjects with death within 28 days will be censored on D29.

Sensitivity analysis:

(1) Imbalances in age, baseline score, use of antiviral drugs such as remdesivir, or IL-6/IL-6R antagonist, or related factors that may affect the results will be investigated with sensitivity analyses and these factors will be evaluated separately in the Cox-Model to assess their potential impact on the primary efficacy endpoint.

(2) Use only data from planned visits to analyze time to improvement in the main analysis.

(3) The days from randomization to the first clinical improvement will be analyzed.

Since there are no available best supportive case (BSC) for this disease, controlling BSC use between two arms is difficult, and consequently there may be imbalance for some particular BSCs between two arms. To evaluate whether there may be some potential bias caused by such imbalance, we will evaluate the percentage of the largest and second largest BSC used in the trial if the difference of such BSC between two arms are significant. Further analyses will be performed to study whether the efficacy results are indeed caused by such differential BSC use between two arms.

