10.4.2. Secondary efficacy endpoints

Proportion of death or respiratory failure, defined as the need for mechanical ventilation, ECMO, non-invasive ventilation, or high flow oxygen devices at D29. Cumulative number of subjects reaching the composite endpoint vs number of people in the ITT population. Chi-square test will be used to compare the difference between the two arms.

For the disease progression, during the observation period, a progression from scale 3 or 4 to scale 2 or 1, or from 2 to 1, is considered as an event. The days from the randomization to the first time point of progression will be defined as time of progression. The probability function of clinical progression will be estimated by Kaplan-Meier method. The median time and its 95% confidence interval for each group will be reported. The 95% confidence interval for the median time will be estimated using the Brookmeyer-Crowley method with log-log function conversion to achieve a normal approximation. The progression rate will be estimated by the layered Cox-Model. Cumulative progression rates estimated by the KM method for day 29 and the 95% confidence intervals will be reported.

All-cause mortality at Day 15 and Day 29: the Mantel-Haenszel stratum-weighted estimator of the risk difference will be used to compare the treatments.

Rate of clinical relapse, defined as proportion of patients who have initially reached score 5 (hospitalized, without oxygen therapy) for more than one day but subsequently become dependent on oxygen support. Since responders are not based on the randomization, a descriptive statistic will be reported and an exploratory analysis using a Chi-square test will be performed.

Improvement rate of clinical status on Days 8 and 15 (proportion of subjects with clinical improvement): percentage of subjects with clinical improvement on Day 8 or 15 in the ITT population. Chi-square test will be used to compare the difference between the two arms.

The discharge time starts from randomization to discharge. T-tests will be used to compare the differences between the two groups in completers.

Duration of each major treatment (days): Descriptive statistics will be analyzed for mechanical ventilation (IMV, NIV), extracorporeal membrane oxygenation, duration of oxygen therapy, and length of hospital stay.

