10.6. Missing Data Convention

We will use the following rules to deal with missing data:

Participants who have not been lost to follow up or experienced the event will be censored at Day 29. Participants without an event but lost to follow-up will be censored at the last date of follow-up.

We will perform two more analyses on the following data sets for the purpose of sensitivity analysis:

First: Participants who have not dropped out or experienced an event are censored at Day 29. Participants not receiving study drug will be excluded from the analysis. Participants without an event but lost to follow-up will be censored at the last date of follow-up. When the event is documented, the time to the event is the length of time from the randomization to the event observed if at least one disease assessment before the event is documented.

Second: Participants who have not been lost to follow up or experienced an event and are followed at the end of the trial will be included. Participants not receiving study drug will be excluded. Participants who have documented the event and have at least one disease assessment(s) will be included.

We will compare the results of the primary analysis with the results from the analyses on the first and second sets, respectively. The impact of missing data and robustness of the primary analysis will be evaluated.

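### Ventilation, ECMO, oxygen and hospital-stay days are summarised with no stated population and no rule for death, so a shorter duration can reflect harm as well as benefit

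*Combined protocol and SAP*

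**What the plan says.** Section 2.2 opens with "Secondary objectives are to compare, for each treatment arm" and goes on to include durations of mechanical ventilation, ECMO and supplemental oxygen, and length of hospital stay. Section 2.5 and the synopsis list each of these, in days, as a secondary endpoint. The oxygen endpoint is restricted by route: "Duration of oxygen therapy (oxygen inhalation by nasal cannula or mask) (days").

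The whole analysis of these items is one sentence in section 10.4.2: "Duration of each major treatment (days): Descriptive statistics will be analyzed for mechanical ventilation (IMV, NIV), extracorporeal membrane oxygenation, duration of oxygen therapy", and then hospital stay. That section does not say whether the summary covers all randomised subjects, only users of the support, or only survivors. It does not say how a death is counted, or how a move from mask to ventilator is counted for oxygen.

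Two other rules come near the point but do not settle it. Section 10.4.1 states "Subjects with death within 28 days will be censored on D29", but this stands among the time-to-event censoring rules, which open with the primary endpoint. Section 10.6 states "Participants who have not been lost to follow up or experienced the event will be censored at Day 29" and otherwise deals only with events, censoring and exclusions. Section 10.3.1 defers detail to a statistical analysis plan, but the documents under review contain no further rule for these durations.

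**The concern.** The trial admits patients at NIAID scores 2 to 4, including patients intubated for up to 7 days, and all-cause mortality is itself an endpoint. Deaths during support and in hospital must be expected. Each death stops the count of ventilator, ECMO, oxygen and hospital days. For oxygen, intubation stops it too, because only cannula or mask days count.

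Take two patients. One has 4 days on a mask, is intubated and dies on Day 10: 4 oxygen days. The other stays on a mask for Days 1 to 9 and goes home on room air on Day 10: 9 oxygen days. The worse course gets the smaller number.

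If by-arm means are read as the comparison that section 2.2 promises, a difference in days cannot be attributed to faster recovery, and it may point away from benefit.

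**Working it through.** There is no figure in the plan to reproduce, since this point concerns how endpoints are defined. The check asks whether more harm can shorten the durations, and whether a death-scored measure restores the direction. The documents give no death rates and no days by type of course, so those inputs are assumptions.

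**Check 1: three patient courses, mean days per randomised patient**

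Assumed days over a 28-day window:
- R, recovers on oxygen: oxygen 8, ventilator 0, stay 11.
- V, ventilated and survives: oxygen 7, ventilator 12, stay 26.
- D, ventilated and dies: oxygen 2, ventilator 6, stay 8.

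The control mix R/V/D is 78/12/10%. The 78% borrows the recovery rate in section 10.1; the rest is assumed. Harm scenario 1 turns half of the ventilated survivors into deaths (78/6/16%). Harm scenario 2 also has more patients deteriorating (70/10/20%).

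Mean = R share × R days + V share × V days + D share × D days. For control:
- Stay: 0.78×11 + 0.12×26 + 0.10×8 = 12.50
- Ventilator, all patients: 0.12×12 + 0.10×6 = 2.04; among the ventilated, 2.04/0.22 = 9.27
- Oxygen: 0.78×8 + 0.12×7 + 0.10×2 = 7.28

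Free days are 28 minus the days used, with death scored 0:
- Ventilator-free: 0.78×28 + 0.12×16 = 23.76
- Hospital-free: 0.78×17 + 0.12×2 = 13.50
- Alive and off all support: 0.78×20 + 0.12×9 = 16.68

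| Measure | Control (10% die) | Harm 1 (16% die) | Harm 2 (20% die) |
|---|---|---|---|
| Stay | 12.50 | 11.42 | 11.90 |
| Ventilator days, all patients | 2.04 | 1.68 | 2.40 |
| Ventilator days, ventilated only | 9.27 | 7.64 | 8.00 |
| Oxygen days | 7.28 | 6.98 | 6.70 |
| Ventilator-free days | 23.76 | 22.80 | 21.20 |
| Hospital-free days | 13.50 | 13.38 | 12.10 |
| Days alive off all support | 16.68 | 16.14 | 14.90 |

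In harm 1 every raw duration looks better than control. In harm 2 stay, oxygen days and ventilator days among the ventilated still look better, but ventilator days over all patients rise, because more patients are ventilated. The sign for ventilation therefore turns on the denominator, which the plan does not state. All three death-scored measures worsen in both scenarios.

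**Check 2: simulation with no change in speed of recovery**

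Time on support T is exponential with the 11-day control median of section 10.1. Death time D is independent and exponential, with an assumed probability of death by day 28. Raw days = min(T, D, 28). Free days = 28 − T if T is below 28 and D exceeds 28, and 0 otherwise. There were 400,000 simulated patients per row.

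| Assumed death probability by day 28 | Mean raw days | Median raw days | Mean days alive and off support |
|---|---|---|---|
| 10% | 12.65 | 10.35 | 13.38 |
| 15% | 12.42 | 10.08 | 12.61 |
| 20% | 12.16 | 9.76 | 11.88 |
| 25% | 11.91 | 9.48 | 11.12 |

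Raw days fall by 12.65 − 11.91 = 0.74 through extra deaths alone, and the median moves the same way. Days alive and off support also fall, which here correctly signals harm. ECMO was not computed separately; death ends its day count in the same way.

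**The case against.** The strongest reply is that little depends on these summaries. They carry no test, p-value or confidence interval, while several other items in section 10.4.2 have a chi-square test, a Mantel-Haenszel estimator or a t-test. The same section separately analyses all-cause mortality at Days 15 and 29, death or respiratory failure in the ITT population, and progression, which counts death. The primary analysis keeps patients who die as non-improvers to Day 29. Excess deaths would be seen. All of this stands and limits the point; it does not make the durations themselves interpretable.

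It can also be said that silence is not a choice. That is right. A reader might infer that the plan has decided to score a death as a short duration, or that a harmful drug would look better. The documents support neither: they leave population and death handling unstated, and the 70/10/20% mix shows harm appearing as more ventilator days over all patients.

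A reader might also infer that a move to high-flow oxygen stops the oxygen count. Appendix A places high-flow devices in a separate category from supplemental oxygen, which makes that reading plausible, but no section says so. The case of intubation is clear.

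Finally, free-day measures need data after discharge. Table 2, note 5, requires daily status only in hospital; after that it comes from study visits. This stands, and the fix has to allow for it.

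**Conclusion.** The concern holds as a gap in specification. Section 2.2 promises a comparison, and section 10.4.2 supplies descriptive days with no population and no rule for death. Counted as written, a shorter duration can come from death and, for oxygen, from intubation.

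The size is illustrative only: about 1.1 days of stay (12.50 − 11.42) and 0.4 ventilator days (2.04 − 1.68) for 6 percentage points more deaths under the assumed courses, and 0.74 days in the simulation across death probabilities of 10% to 25%. The mechanism does not need these particular values, but the net direction depends on the mix of courses and on the denominator.

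The effect is limited to descriptive secondary summaries. It does not touch the primary analysis or the separate analyses of mortality, death or respiratory failure, and progression. This is a worthwhile and inexpensive improvement, not a threat to the trial's main conclusion.

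**What to change.** In section 10.4.2, report by arm, in all ITT subjects, over the 28 days from randomization, the days alive and free of:
- (a) IMV/NIV;
- (b) ECMO;
- (c) any supplemental oxygen or respiratory support;
- (d) hospital.

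Score death by Day 29 as 0. Add two data rules:
- **After discharge:** carry status between scheduled visits, and count home oxygen under scale 7 as oxygen. Scale 7 also covers limited activity without oxygen, so use the respiratory-treatment record from the visit, not the score alone.
- **Loss to follow-up:** state how days after the last contact are counted. The rule should also cover patients whose last visit falls before Day 29, since that visit has a window of ±3 days in section 7.2.2 and ±4 days in section 3.1.

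Keep the planned raw durations as supporting summaries split by survivors and deaths, with the number of users in each arm.

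The cost is wording and programming. In-hospital status and respiratory support are already recorded daily, so no new collection is needed there. There are two downsides: the measure mixes mortality with duration, so its components should be reported alongside, and oxygen days after discharge will be approximate.

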3. STUDY DESIGN

3.1. Study Design Overview

This is a Phase III randomized double-blind placebo controlled multi-site study to compare two COVID-19 treatment regimens in hospitalized adult subjects who are diagnosed with severe COVID-19.

Arm A: CD24Fc/Best Available Treatment;

Arm B: placebo/Best Available Treatment.

CD24Fc will be administered as single dose of 480mg via IV infusion on Day 1. Total of 270 subjects will be enrolled and randomized in 1:1 ratio to receive CD24Fc or placebo. All subjects will be treated with the best available treatment. The follow up period is 28 days. Those who uses immune modulators such as IL-6/IL-6R antagonists or experimental antiviral drugs are allowed to participate the trial.

Phase III study consists of screening period and treatment/follow up period. Each subject should have 6 visits. Visit 1 (D-3 to D-1); Visit 2 (D1); Visit 3 (D4); Visit 4 (D8±1d); Visit 5 (D15±2d), Visit 6 (D29±4d).

If the patient's clinical status improves and is discharged to home care, the follow up visits can be carried out through telemedicine (phone or video interviews). The clinical investigators should make best efforts to obtain the vital signs, clinical status evaluation, concomitant medicines and adverse events assessment. The laboratory tests, radiology study, ECG and research samples are optional if the patient is discharged.

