Absolute Lymphocyte Count: patients' dynamic changes in absolute lymphocyte count during the treatment / observation period will be monitored to assess the possible correlation between lymphocyte levels and disease outcome and prognosis.

D-dimer levels: patients' dynamic changes in D-dimer levels during the treatment / observation period will be monitored to assess the possible correlation between lymphocyte levels and disease outcome and prognosis.

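### Section 10.4.2 prespecifies no between-arm comparison for absolute lymphocyte count or D-dimer, both listed secondary endpoints, and its D-dimer paragraph names the wrong marker

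*Combined protocol and SAP*

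**What the plan says.** The secondary endpoint lists in the synopsis and in Section 2.5 include "Absolute lymphocyte count" and "D-dimer concentration in the plasma". Section 2.2 frames the secondary objectives as comparisons of the treatment arms, and its list ends with "the changes in absolute lymphocyte count and markers of inflammation". D-dimer is not named there. It appears in Section 2.3, where the exploratory objectives concern the effect of CD24Fc on "systemic steroid dosage, inflammatory cytokine changes, D-dimer level changes, lymphocyte subtype distribution".

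The efficacy analysis of the two markers is a pair of short paragraphs at the end of Section 10.4.2, one for ALC and one for D-dimer. Both say that changes in the marker "will be monitored to assess the possible correlation between lymphocyte levels and disease outcome and prognosis". Neither names an arm contrast, test, model, time point or baseline adjustment.

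Section 7.1.5 schedules laboratory tests at screening, D1, D4, D8 and D15. Section 3.1 then says: "The laboratory tests, radiology study, ECG and research samples are optional if the patient is discharged". Footnote 7 to Table 2 is slightly firmer: it advises the post-discharge tests without making them mandatory.

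**The concern.** An objective that compares arms needs an analysis that compares arms. Correlating a marker with outcome shows whether the marker is prognostic. It does not show whether CD24Fc changes the marker. Followed as written, the plan yields no treatment-effect estimate for either endpoint, and the stated D-dimer analysis concerns a different marker. ALC is not incidental here: Sections 1.2 and 1.5 present prevention of lymphopenia as part of the drug's rationale.

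Leaving the comparison open also leaves open how missing values are handled. Tests become optional at discharge, and the trial expects CD24Fc patients to recover sooner. A comparison of whatever values exist at a late visit would therefore be made in groups selected by outcome, to a different degree in each arm.

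**Working it through.** **1. Is there an arm comparison elsewhere?** The places that could supply one are as follows.
- Section 10.4.2, other endpoints: chi-square tests, a t-test and a Mantel-Haenszel risk difference are written out for several of them. The treatment-duration endpoints get descriptive statistics only. The two laboratory endpoints get neither an arm comparison nor an efficacy summary by arm.
- Section 10.4.4: a descriptive safety summary of laboratory tests and their changes from baseline.
- Section 10.6: censoring rules for time-to-event data, with no rule for missing laboratory values.
- Section 10.3.1: defers detail to a statistical analysis plan. The supplied text contains no further analysis of these markers.

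The documents state no sample size, power or alpha for ALC or D-dimer, so there is no figure of the plan's own to reproduce.

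**2. How large could the missingness be?** Inputs from Section 10.1 are exponential times with medians of 11 days (control) and 7.14 days (CD24Fc). Section 3.2 gives 135 patients per arm. D8 is 7 days and D15 is 14 days after randomization.

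P(improved by t) = 1 − 2^(−t/median)
- D8: 1 − 2^(−7/11) = 35.7% control; 1 − 2^(−7/7.14) = 49.3% CD24Fc.
- D15: 1 − 2^(−14/11) = 58.6% control; 1 − 2^(−14/7.14) = 74.3% CD24Fc.

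Improvement means scale 5 or above, and scales 5 and 6 are still in hospital. Let f be the share of improvers who have been discharged and have no test. The documents do not give f, so a range is shown. Patients with a value = 135 × (1 − f × P).

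| f | D8, control v CD24Fc | D15, control v CD24Fc |
|---|---|---|
| 50% | 111 v 102 | 95 v 85 |
| 75% | 99 v 85 | 76 v 60 |
| 100% | 87 v 68 | 56 v 35 |

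Example: at D15 with f = 75%, control is 135 × (1 − 0.75 × 0.586) = 76 and CD24Fc is 135 × (1 − 0.75 × 0.743) = 60.

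**3. What bias could follow?** Take the worst case (f = 100%) and a marker on which the drug has no effect, scaled so that higher is better. Assume a correlation ρ with speed of recovery; ρ is not in the documents. With p the proportion not improved, the mean among those observed is −ρ φ(Φ⁻¹(p))/p in SD units. At D15, p is 0.414 and 0.257.
- ρ = 0.2: −0.188 v −0.251, a difference of −0.06 SD.
- ρ = 0.3: −0.282 v −0.376, a difference of −0.09 SD.
- ρ = 0.5: −0.471 v −0.627, a difference of −0.16 SD.

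At D8 the same calculation gives −0.04, −0.06 and −0.10 SD. In each case CD24Fc looks worse than it is.

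**4. Limits of this sizing.** The medians imply 28-day improvement of 82.9% and 93.4%, an average of 88.1%, whereas Section 10.1 assumes 78% recovery. The improvement shares may therefore be too high. The counts with values also include patients who died before the visit, who have no value.

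**The case against.** The strongest reply is that these are the last two endpoints on a long list, with no alpha or power attached. D-dimer also belongs to the coagulation tests in the safety laboratory set, so Section 10.4.4 would summarise it. The word lymphocyte in the D-dimer paragraph is an evident copying slip, and Section 10.3.1 leaves detail to a later plan. All of this is fair as to weight. None of it supplies a between-arm efficacy comparison, and what Section 10.4.2 states is a different analysis, not just an incomplete one.

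Several stronger readings are tempting, but the documents do not support them.
- A reader might infer that Section 2.2 requires the arms to be compared on D-dimer. It does not name D-dimer. The defect there is a mismatch between a secondary endpoint and an exploratory objective.
- A reader might infer that D-dimer has no analysis at all. Its changes are to be followed and the safety summary can cover it. What is missing is a correctly named efficacy analysis.
- A reader might infer that the plan sets up a biased raw comparison at D15. It proposes none; the bias is a risk if the gap is filled naively.
- A reader might take 56 v 35 as the expected D15 numbers. That needs every improver to be discharged and none to be tested, although some improvers remain in hospital and post-discharge tests are advised.
- A reader might conclude that no valid comparison is possible. In-hospital tests run to D15, so one can be specified.

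**Conclusion.** The point holds in this form: no between-arm comparison is prespecified for ALC or D-dimer, the D-dimer paragraph names the wrong marker, and D-dimer's standing as secondary or exploratory is unresolved. These follow from the text and need no assumptions.

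The missingness argument is conditional. If recovery times follow the planned medians, missing D15 values would be 29% v 37%, 44% v 56% or 59% v 74% (control v CD24Fc) as the share of improvers discharged without tests goes from 50% to 75% to 100%. The resulting bias in a naive comparison is modest, at most about 0.06 to 0.16 SD at D15 for assumed correlations of 0.2 to 0.5, and it runs against the drug. The primary endpoint is not affected. The point is worth correcting because it is cheap and because ALC change is part of a stated comparative objective.

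**What to change.** Before unblinding, replace the two paragraphs in Section 10.4.2 as follows.
- **Main analysis:** a baseline-adjusted comparison of the arms on log values, for example a mixed model for repeated measures with baseline log value, baseline score, arm, visit and arm-by-visit. Take D8 as the main contrast, since less is missing there than at D15. An analysis of covariance at D8 would be a reasonable simpler choice.
- **Visits:** D4, D8 and D15 for ALC; D8 and D15 for D-dimer. Section 7.1.5 includes coagulation tests at D4 but the Visit 3 list in Section 7.2.2 omits them. These must be reconciled before a D4 contrast for D-dimer is planned.
- **Missing values:** the mixed model assumes data missing at random, so add a sensitivity analysis for values missing after discharge, for example imputation from baseline and the recorded clinical course. State separately how deaths are handled.
- **Wording:** change lymphocyte to D-dimer in the second paragraph, keep the correlations as exploratory, and make D-dimer's status the same in Sections 2.2, 2.3 and 2.5 and in the synopsis.

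The cost is plan wording and a little programming. The D8 and D15 contrasts need no new samples.
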